4. Reducing intolerance of Uncertainty

Participants will complete between 1 and 4 sessions on each module depending on clinical need guided by their assessment and formulation. Treatment duration will be a maximum of 16 sessions. Therapists will complete a checklist at the end of each session to indicate which parts of the treatment intervention were covered in the session. Please see Appendix C for Treatment Fidelity Checklist developed by Parr et al. (2020) which will be adapted specific for this intervention.

Participants will be asked to consent to the video recording of treatment sessions to be reviewed by members of the research team for the purpose of ensuring quality of treatment and adherence to the treatment protocol. If a participant does not consent to the video recording of sessions then they can still be included in the study. Consent to video-recording will be captured on the consent form.

In addition to being asked to consent to video-recording of the session on the consent form, this will be reviewed at each treatment session. It is made explicit in the PIS that a participant can request that a recording can be stopped at any point and deleted. Ongoing consent to video record sessions will be recorded in the clinical notes along with any requests to stop recording individual sessions. Consent to recording individual sessions or declining the recording of sessions will be recorded on the clinical record of the participant for each session.

A proportion of the recorded treatment sessions will be watched and rated by a member of the research team using the treatment fidelity checklist (Appendix C). The therapist and raters' checklists will then be compared to establish fidelity to treatment model. All recordings will be deleted at the end of the study.

To evaluate the treatment's credibility and satisfaction, participants will be given a feedback questionnaire to complete. This will be based on those used in previous programmatic Intolerance of Uncertainty research projects (Bentley et al 2020) Please See Appendix D.

4.4 Data Analysis:

Data analysis on primary outcome measures will use visual analysis which is traditional for quantitative single-case methodology (Morley, 2018, p 88). Tau-U will be used to measure data non overlap between the phases using an online calculator

at <http://www.singlecaseresearch.org/calculators/tau-u> (Parker, Vannest, Davis and Sauber, 2011).

4.4.1 Primary Outcomes:

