5. SAMPLE AND RECRUITMENT

5.1 Sample Size

Replication will be sought across three to six participants. Three replications are the conventional minimum number to establish an effect (Morley, 2018 p 158). Recruiting up to six participants allows for attrition and to still meet the minimum number of 3 at the same time as ensuring as few participants as necessary are exposed to the novel treatment intervention.

The number of participants will be determined by:

a) pragmatic constraints including time available following ethical approval

b) participant recruitment

c) number of therapists implementing the treatment protocol.

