5.3 Consent

Participants will be required to voluntarily give fully informed consent. They will be informed about the research through the participant information sheet (PIS) and will be given at least 48 hours to consider their participation and to discuss this with significant others. Potential participants will be given the opportunity to discuss with any queries they may have or obtain clarity on any matter. Once they are satisfied that they are fully informed about the study the written consent form will be completed with the participant by the chief investigator. If participants have expressed a wish for remote delivery of treatment then an electronic consent form will be completed via Qualtrics.

Participants will be informed that they can withdraw from the study at any point without having to give a reason.

Consent to continue participation in the research study will be reviewed at each contact with the participant and documented on the session summary sheet and in clinical records.

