6.3 Potential risks and Burdens

6.3.1 Distress:

As with any psychological therapy intervention there is the potential for it to be distressing to the participant when discussing their problems. However, this is no

greater than the potential for this to happen in alternative psychological treatment they would receive as usual. Participants will be advised of this in the participant information sheet. The research therapists conducting the treatment are qualified CBT therapists with skills and experience working with people in distress and will help manage the distress in the session. The hope is that as with other psychological therapies, distress will reduce through the course of therapy.

If distress does not reduce and mental health deteriorates during the course of therapy therapists will seek appropriate supervision and options would be discussed explicitly with the participant including withdrawal from the research and referral for additional/alternative support and treatment.

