Appendix B- Overview of treatment phases including interventions and duration

Appendix C- Treatment Fidelity Checklist

Personalised Anxiety Treatment – Autism (PAT-A)

Session Recording Form

Participant ID:	Therapist:
Date:	Session:
Initial Treatment Plan:	
Current Treatment Plan:	
SUPERVISION:	
Has this case been discussed since the last session?	YES NO
Were changes to the treatment plan discussed?	YES NO
What was the main conclusion from Supervision?	
Continue with current plan	
Adjust current plan	Specify:
	Specify:

Change treatment plan	
Additional information/supervision notes:	

Session Recording Form Continued...											
Participant ID:	Therapist:										
Date:	Session:										
Research Information:											
Did the participant attend the session?											

 
 YES	NO	
 
 		
 
 		
 
 		
 
 		
 
	YES	NO									
If No please detail the reasons for this if know

YES	NO										
											
											
											
											

Did the participant consent to ongoing inclusion within the PAT-A trial?																					

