	Not applicable	Issue is considered to be of no or minimal concern	Issue is considered to raise moderate concerns	Issue is considered raise high levels of concern	For issues raising moderate or high levels of concern, indicate how will they be managed Note: It would be good practice to explain why a specific issue is of no or minimal concern, rather than simply tick the box.
Burden to participants					Participants will be advised that will all psychological therapies there is a potential for distress when discussing their difficulties however this is no different from the treatment they will be on the waiting list to receive. The main burden is time taken to complete daily diaries and other outcome measures. Participants will be informed of the likely time commitment required within the Participant Information Sheet (PIS) and will be re compensated for this time using a Wage Payment Model.
Use of personal material in dissemination of research (e.g. quotations)					Personal quotes will not be included in the dissemination of the research.
Descriptions of specific participants in dissemination of research					Participants will be referred to by pseudonyms. Care will be taken that combination of demographics (age, gender, and ethnicity) will not make a person identifiable. Some background information will be included to provide context of the participants but non-essential information will be omitted or changed to maintain anonymity.
Other:					Please specify: Right to Withdrawn As in any other psychological therapy participants will be given the right to withdraw during the study without having to provide an explanation. They can return to their prior place on the waiting list to access treatment as usual. If participants withdraw they will be asked for permission to still use their data however this is entirely optional and they can decline.

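### Does the plan's silence on participants who withdraw during treatment undermine its count of three replications?

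*Combined protocol and SAP*

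**What the plan says.** Section 5.1 (Sample Size) states that "Replication will be sought across three to six participants" and justifies the lower figure by convention: "Three replications are the conventional minimum number to establish an effect". The upper figure is there to absorb loss: "Recruiting up to six participants allows for attrition and to still meet the minimum number of 3". It gives no attrition rate.

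Section 4.4 (Data Analysis) plans visual analysis of the daily diary, with Tau-U for non-overlap between phases. Section 4.4.1 lists the features to be examined and adds an independent second rater. It does not confine the graphs to people who finish, and it sets no number of replications that would count as success.

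On withdrawal, 5.3 allows it at any time without a reason. Under 6.3.1, if distress fails to fall and mental health worsens, therapists seek supervision and "options would be discussed explicitly with the participant including withdrawal from the research". Appendix E says: "If participants withdraw they will be asked for permission to still use their data however this is entirely optional and they can decline".

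On records, 5.3 has continued consent "reviewed at each contact with the participant and documented on the session summary sheet and in clinical records". The session form in Appendix C asks "Did the participant consent to ongoing inclusion within the PAT-A trial" and requests reasons if not. That form comes from another trial; 4.3 describes it as a checklist "which will be adapted specific for this intervention".

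**The concern.** In a single-case series the strength of the claim depends on how many cases were tried as well as how many showed the effect. Three out of three is a stronger result than three out of six, yet 5.1 names a count with no denominator. The plan also tolerates heavy loss: six can fall to three and the minimum is still met.

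That loss may be related to outcome. Withdrawal is one of the options raised with a participant who is deteriorating, and a leaver may refuse further use of their data. If the people who leave are those in whom the treatment did nothing, the remaining cases give too favourable a picture, and a reader shown only those cases could not tell. The main conclusion of the pilot would then be at stake.

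**Working it through.** **Inputs.** From 5.1: three to six participants and a minimum of three replications. The documents give no attrition rate and no probability that a single case looks like a replication when the treatment does nothing. That probability, *f*, is assumed here to lie between 0.1 and 0.3, with independent cases.

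**The plan's own figure.** Going from six to three is a loss of 1 − 3/6 = 50%, and 3/(1 − 0.5) = 6. The allowance is therefore arithmetically coherent. With six enrolled, the chance that at least three remain is 0.98 at 20% independent dropout and 0.66 at 50%.

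**Effect of the denominator.** Suppose three remain and all three replicate:

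| Started phase B | Left | Share of those remaining | Share of starters |
|---|---|---|---|
| 4 | 1 | 3/3 = 100% | 3/4 = 75% |
| 5 | 2 | 3/3 = 100% | 3/5 = 60% |
| 6 | 3 | 3/3 = 100% | 3/6 = 50% |

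These shares need no assumption beyond the plan's own range.

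**Effect of who leaves (illustrative).** Six start, exactly three leave, and the event is that all three who remain look like replications by chance.

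| Who leaves | Formula | *f* = 0.1 | *f* = 0.2 | *f* = 0.3 |
|---|---|---|---|---|
| Unrelated to outcome | f³ | 0.001 | 0.008 | 0.027 |
| Cases without an effect first | P(Binomial(6, f) ≥ 3) | 0.016 | 0.099 | 0.256 |
| Cases with an effect first | f⁶ | 0.000001 | 0.00006 | 0.0007 |

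The second row is the worrying one, about 16 to 9.5 times the first. It is one extreme, and the first row is not the other: loss could also run the opposite way, as in the third row.

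A less extreme version lets each case without an effect withdraw with probability *w* while cases with an effect all stay. The chance that at least three finish and every finisher looks improved is the sum over x = 3 to 6 of C(6, x) · fˣ · [(1 − f)w]⁶⁻ˣ. At f = 0.3 this is 0.0007 for w = 0, 0.044 for w = 0.5 and 0.12 for w = 0.75. The event differs slightly, because the number of leavers is not fixed at three, but it shows how much of the 0.256 depends on perfectly selective loss.

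**What the text supports.**

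- *Is there a results rule to bias?* The three appears only in the sample-size section, as a reason for how many to recruit. Section 4.4 does not turn it into a pass mark.
- *Is anyone to be dropped?* No passage says so. Section 4.4.1 plots diary data without a completers restriction, 6.5 has all participants choose a pseudonym for the write-up, and Appendix E's request for permission makes sense only if leavers' data are meant to be used.
- *Is withdrawal tied to absence of effect?* Only loosely. Section 6.3.1 requires both that distress does not fall and that mental health worsens; supervision is sought, and withdrawal is one of several options. Appendix E rates the likelihood of harm, including deterioration, as low, although it rates stress as medium.
- *Can a leaver be analysed?* Yes, where data use is allowed. The 14 to 28 day baseline in 4.1 supplies a phase A against which a shortened phase B can be compared.

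**The case for a change.** The strongest contrary argument is that three replications is the nearest thing the plan has to a criterion for an effect. A denominator fixed in advance would remove a choice that could otherwise be made after the results are known, at the cost of a sentence. Some cases may also be unrecoverable: a deteriorating participant can withdraw, refuse data use and vanish from the graphs. The session form that would record reasons belongs to another trial, and its fields may not survive adaptation.

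Some of this stands. The documents do not state the denominator, loss related to outcome is possible, and a reader would want to know how many people started. But a sentence in the plan would not recover data that a participant has declined to release, and continued consent is documented under 5.3 whatever happens to the form. A table listing each leaver with phase reached and reason has its own cost: with six or fewer people from one Trust it meets the undertaking in 6.5 to broaden or omit details that could identify someone.

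**Conclusion.** The gap is real but it is one of reporting detail, and analysts can be expected to fill it sensibly. Following the plan as written gives no wrong result: it contains no completers-only rule, no threshold in the analysis section, and a stated intention to seek leavers' permission to use their data. In a series of at most six individually graphed cases, stating how many started is ordinary practice.

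The size that can be stated without assumption is the change of denominator: three replicating cases are 75%, 60% or 50% of four, five or six starters. The chance probabilities, including 25.6%, rest on an assumed per-case rate, independence, loss of exactly half and wholly selective withdrawal. They show that selection can matter in a small series, not that it does so here. The conclusion assumes that the authors report all starters. The consent pages were not available, and Appendix E's grid (15/06/2020) predates protocol V1.3 (04/02/22), so the current terms on data kept after withdrawal could not be confirmed. No change to the plan is called for.

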5.2 Recruitment

Participants will be initially recruited from the Rheumatology Department within Newcastle Upon Tyne Hospital Foundation NHS Trust. If the sample size is not reached within the Rheumatology Department, then recruitment will commence in the Gastroenterology Department. Participants will be those experiencing distress associated with the adjustment to their long-term health condition and those who would be referred to the Psychology in Healthcare Department for psychological intervention (treatment as usual). The healthcare team will be briefed of the purpose of the study and inclusion/exclusion criteria in order to identify potential participants. The healthcare team will then identify any potential participants in their routine consultations and introduce the research study and seeking expressions of interest to find out more about participating in the research. Verbal consent will be obtained to pass contact details to the research team and this will be recorded in the participants' electronic medical record. Expressions of interest will be passed to the research team and potential participants will then be contacted and given verbal and written information (Participant information sheet) about the study.

Participants will be screened by the research therapist(s) through a short interview process in line with eligibility criteria and using standardised questionnaires. Those who are screened who are not suitable for participation in the research trial will be

offered alternative psychological therapy for their difficulties via the multi-speciality psychology in health care team. This is 'treatment as usual' for patients experiencing difficulties adjusting to health problems.

5.3 Consent

Participants will be required to voluntarily give fully informed consent. They will be informed about the research through the participant information sheet (PIS) and will be given at least 48 hours to consider their participation and to discuss this with significant others. Potential participants will be given the opportunity to discuss with any queries they may have or obtain clarity on any matter. Once they are satisfied that they are fully informed about the study the written consent form will be completed with the participant by the chief investigator. If participants have expressed a wish for remote delivery of treatment then an electronic consent form will be completed via Qualtrics.

Participants will be informed that they can withdraw from the study at any point without having to give a reason.

Consent to continue participation in the research study will be reviewed at each contact with the participant and documented on the session summary sheet and in clinical records.

5.4 Eligibility Criteria

5.4.1 Inclusion criteria

- Age 18- 65
- Diagnosed long term health condition (Rheumatoid Arthritis, IBS/IBD)
- Minimum of 12 months since diagnosis of physical health condition
- Difficulties adjusting to long term health problems.
- Willingness to engage with psychological treatment to manage distress associated with their health condition.
- Fluent English speaking

5.4.2 Exclusion criteria

- Under 18 or over 65
- Multiple long term health conditions
- Progressive long term health conditions
- Experiencing mental health difficulties which may affect ability to engage with time-limited psychological therapy including diagnoses of Major Depressive Episode and/or severe and enduring mental health problems, comorbid substance misuse and suicidality.
- Diagnosis of Autism Spectrum Disorders (ASD)
- Non-English speaking

5.5 Clinical Considerations

Participants accessing treatment through the trial are those who would wait to access treatment through the Psychology in Healthcare department in the acute hospital setting or access treatment for their distress separately through mental health services. Participants will be informed that whilst this treatment is based on

empirical evidence and an extension of previous treatment models targeting IU this specific treatment model is new. Participants will be informed that if they chose to withdraw at any time there will be an arrangement in place so that they can access their original place on the waiting list without penalty to receive usual care or be referred to access alternative treatment if they were not already on the waiting list.

6. ETHICAL AND REGULATORY COMPLIANCE

6.1 Regulatory Review

An application will be made for Health Research Authority (HRA) and Research Ethics Committee (REC) approval involving submission of the protocol and all research documentation.

6.2 Scientific Review

The scientific quality of the project has been reviewed by an independent panel at Newcastle University.

It has also been reviewed by experienced members of the research team and the project research supervisor.

See Appendix E and F for the Ethics Grid and Diversity Grid required for approval by University.

6.3 Potential risks and Burdens

6.3.1 Distress:

As with any psychological therapy intervention there is the potential for it to be distressing to the participant when discussing their problems. However, this is no

greater than the potential for this to happen in alternative psychological treatment they would receive as usual. Participants will be advised of this in the participant information sheet. The research therapists conducting the treatment are qualified CBT therapists with skills and experience working with people in distress and will help manage the distress in the session. The hope is that as with other psychological therapies, distress will reduce through the course of therapy.

If distress does not reduce and mental health deteriorates during the course of therapy therapists will seek appropriate supervision and options would be discussed explicitly with the participant including withdrawal from the research and referral for additional/alternative support and treatment.

6.3.2 Burden

The main burden for participants is the time involved in participation in the research. From the start of baseline monitoring to follow up will be up to 25 weeks. During active treatment participants will be required to commit one hour per week for therapy sessions for up to 16 weeks, however this is no different from standard psychological therapy. Standardised questionnaire measures will be completed at various points during the treatment however this is standard practice for psychological therapies. The additional burden arises as a result the time taken to complete daily diaries which are specific to the research project. Participants will be required to complete daily diaries for a maximum of 175 days of which these measures take approximately 5 minutes daily. Participants will be informed of the likely time commitment required within the Participant Information Sheet (PIS) and will be able to make an informed decision whether they want to participate. They will be compensated for this time using a Wage Payment Model (Dickert & Grady, 1999)

reimbursing them for the time taken to complete measures in the form of vouchers - see section 6.4 Incentives and rewards below.

6.3.3 Disclosures and discovery of information that may need acting upon:

Whilst it is not anticipated there is a small chance that disclosure of information to or discovery of information by the therapist may need acting upon such as risks to self-and/or others. In the case of this occurring the research therapists will follow standard service protocols. Participants will be explicitly advised at the start of the treatment intervention that if this were to occur that confidentiality would be broken. If it is safe to do so the participant will be advised that the information will be shared and with whom. The researcher will have access to contact details for participants GP, local Crisis Team, local social care duty teams. Support and advice will be sought from the clinical supervisor attached to the research project. Research therapists are qualified CBT therapist who are skilled and experienced with dealing with such disclosures and discovery of information in their everyday roles.

